9.1.1 Economic evaluation

The cohort sample will not be included in the economic evaluation except for the purpose of validation and estimating the representativeness of cost and benefit data for trial participants.

9.1.1.1 Perspective of the study

The economic evaluation will address the study question from a societal perspective with a focus on health service and families³⁶.

9.1.1.2 Measure of benefits used and study type

Cost consequences analysis (CCA), cost-effectiveness analysis (CEA) and cost utility analysis (CUA) will be conducted. In CCA, all the outcomes used in the clinical study will be adopted as measures of benefits, including the QoL dimensions. In CEA, the benefits will be measured by the number of events of recurrent sore throat and the number of symptom-free days. In CUA, different health outcomes will be combined with QoL dimensions.

9.1.1.3 Resources data collected within the trial and costing methods

Medical resource data will relate to the interventions under investigation, any use of health care services due to 'sore throat' episodes not averted, treatment of drug side-effects, surgery complications and long term sequelae. Services to be monitored include: outpatient visits and hospitalisations, investigations, A&E admissions, visits and telephone consultations to and from the GP and any other health care professionals, use of medications (including antibiotics, analgesics, and drugs to manage antibiotic side-effects), and any other use of health care services in both the private and public sectors. Manpower data will be collected separately for each main category of staff. Participants' out of pocket expenses such as over the counter medicines will be reported.

Costing of health care resources will be undertaken in a parallel study and a mixed approach using micro-costing and gross-costing methods will be used³⁷. We will cost resources using health service pay and price data. Where appropriate, these will be integrated using national published data^{38 39 40}. Where relevant, costs will be broken down into capital, staff, consumable and overhead costs. This will aid the production of different cost scenarios.

The impact of the interventions on the time 'invested' by children and carers because of illness, treatment and rehabilitation will also be assessed. Children's days of restricted activity and their level of functioning; time off school; carers' time off work; children's and carers' time involved in outpatients attendance (such as travel time, waiting time and the duration of the clinical visit) and impact on children's and carers' quality of life will be monitored. For carers' in paid/unpaid work, time will be valued in monetary terms. Costing will be undertaken using the human capital approach and the friction cost method⁴¹. Those resources for which we find a statistically significant difference between the groups will be costed. Those which show no statistically significant difference but are of practical significance in their contribution to costs, will also be costed.

The cost analysis will not differ across the different types of economic evaluations. However in the CUA, when carers' preferences will be assessed, particular caution will be used to avoid double counting the loss of income due to work absences ⁴².

Whenever applicable, a discount rate of 6% will be used, which is the rate currently used by the public sector in the UK. Costs will be expressed in UK pounds sterling. Costs will be expressed in the prices of the year in which the final analysis will be carried out and if necessary inflation method will be used to update costs data.

9.1.1.4 Resources/costs data collected outwith the trial

The study is not powered to detect significant differences for rare events. Given the relatively low incidence of surgical complications, long-term sequelae due to surgery and drugs side-effects, data on the related use of resources, costs to the carers and impact on children will be gathered outwith the trial, from the literature and from experts' opinions. 'Consensus' estimates will be obtained by interviewing a panel of experts, including members of the study team and others. The source of the data will always be explicitly stated.

9.1.1.5 Synthesis of costs and benefits

Depending on the outcome measure, if there is no statistically significant evidence that one treatment strategy is more effective than another, a cost-minimisation framework will be used and the less expensive form of care will be recommended. If one strategy appears to be dominant (i.e. to be more effective and less costly than the alternative), the uptake will be

recommended. If one form of care appears to be more effective and more expensive than the comparator, estimates of incremental cost-effectiveness (and cost-utility) ratios will be generated. A judgement will be required in a policy making context to establish whether the additional benefits should be achieved sustaining the additional costs. In any case, recommendations will be made taking into account the generalisability of the results.

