9.1.1.6 Sensitivity analysis

To handle uncertainty not related to sampling variations and to enhance the generalisability of the results, one-way; multi-way and extreme scenario analysis will be undertaken as appropriate and confidence intervals for cost-effectiveness ratios will be estimated under different scenarios ⁴³. A sensitivity analysis taking into account differences in resource use which are practically significant (i.e. potentially costly) but which have not been shown to be statistically significant, will also be undertaken. The sensitivity analysis will also make explicit all the simplifying assumptions made to collect the data⁴⁴.

The application of discounting to the benefits will also be tested in the sensitivity analysis, as well as a range of discount rates. Particular attention will also be given to whether the costs data used reflect the true marginal opportunity costs of the resources used. When more than one reliable source of information is available, such data will be used as a term of comparison. The use of different costing methods for multi-centre studies will be explored.

Earlier studies²⁸⁻³¹suggest that longer term outcomes such as reduction in recurrent sore throat may show only marginal benefits. An equivalence trial with a substantially larger sample size would be necessary to capture significant longer-term outcomes. To contain the cost of the trial we have not proposed a three year follow up. However, the future sequence of clinical events and economic impact will be modelled beyond 2-year follow-up. The relevant data will be derived from studies which will be available and experts' opinions.

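### The economic plan recommends the cheaper care when an effectiveness difference is not statistically significant, in a trial not designed to show equivalence

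*Protocol*

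**What the plan says.** Protocol section 9.1.1.5 sets out how costs and benefits will be combined. Its first branch, which opens by noting that it depends on the outcome measure, covers the case where neither strategy is shown to be more effective at the level of statistical significance. In that case "a cost-minimisation framework will be used and the less expensive form of care will be recommended". A dominant strategy is recommended outright. Incremental ratios are generated only where one form of care appears both more effective and more expensive. The section ends with one general qualifier: "In any case, recommendations will be made taking into account the generalisability of the results". Precision of the effect estimate is not mentioned.

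Section 9.1.1.2 makes several outcomes relevant. The cost-consequences analysis takes all the clinical outcomes and the quality-of-life dimensions, the cost-effectiveness analysis uses sore-throat events and symptom-free days, and the cost-utility analysis combines outcomes with quality of life.

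On costing, section 9.1.1.3 has two limbs: "Those resources for which we find a statistically significant difference between the groups will be costed", and then "Those which show no statistically significant difference but are of practical significance in their contribution to costs, will also be costed". Section 9.1.1.6 takes up the second group again: "A sensitivity analysis taking into account differences in resource use which are practically significant (i.e. potentially costly") but not statistically significant is to be undertaken.

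**The concern.** Failing to reject the hypothesis of no difference is not evidence that two treatments are equally effective. It may only mean that the estimate is imprecise. Cost-minimisation rests on equal effectiveness, and the rule in 9.1.1.5 reaches it through a non-significant test alone. From there, cost alone decides the recommendation, and the observed effect with its interval drops out.

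Section 2.1 makes cost-effectiveness the key research question, so this rule bears on the trial's main message. The section also does not say which outcome governs if they disagree. One outcome could trigger the cheaper-care recommendation while another shows a benefit.

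A smaller issue concerns the costs. Which non-significant resource items count as practically significant is left without a threshold, and the two sections do not make clear whether those items belong in the base case or only in a sensitivity analysis. Under cost-minimisation, the base-case cost difference is what settles the recommendation.

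**Working it through.** **Inputs from the protocol**
- Section 10.1: 142 completers per arm; 5% significance; 80% power; 1.5 days per year of missed schooling with SD 4.5; effect size 0.33 for psycho-social outcomes including quality of life; effect size about 1.0 for the primary outcome; SD about 2.0 for sore throats per year.
- Section 4.3: 30% attrition, 406 recruited.
- Section 1.3: one published benefit of 0.5 to 1 episode per year over two years; in another earlier trial, 1 in 3 controls had surgery.
- Section 10.2.1: controls who later have surgery stay in the control group for analysis.

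**Assumptions:** two-sided test (sidedness is not stated, but two-sided reproduces the sample size); normal approximation; the yearly SD of 2.0, which the protocol uses for age strata, applied to the whole-trial comparison.

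**1. The plan's own figure.** n per arm = 2 × (1.96 + 0.842)² × (4.5/1.5)² = 2 × 7.85 × 9 = 141.3, so 142. Total 284, and 284/0.70 = 405.7, so 406. Both reproduce. This is a superiority calculation.

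**2. Precision.** The 95% interval half-width is 1.96 × 4.5 × √(2/142) = 1.05 school days per year, or 1.96 × √(2/142) = 0.23 SD. An estimate of 1.0 day would have an interval of about −0.05 to 2.05. It is non-significant, yet the interval contains the 1.5 days on which the trial was sized.

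**3. Chance that the trigger is met although a real difference exists.** For a standardised effect d, the probability of non-significance is 1 − Φ(d × √(142/2) − 1.96), where √71 = 8.43.

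| True effect | d | d × 8.43 | Non-significant |
|---|---|---|---|
| 1.5 school days/year, SD 4.5 | 0.333 | 2.81 | 19.8% |
| Quality of life, section 10.1 | 0.33 | 2.78 | 20.6% |
| 0.5 sore throats/year, SD 2.0 | 0.25 | 2.11 | 44% |
| 1 sore throat/year, SD 2.0 | 0.50 | 4.21 | 1.2% |
| Primary outcome as anticipated | 1.0 | 8.43 | about 0% |

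School absence is listed among treatment impacts in Table 2, not among the clinical outcomes. It is shown because it sized the trial and is the same standardised size as the quality-of-life effect.

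**4. Crossover (assumed).** The protocol gives no expected crossover rate. Suppose one third of controls have surgery, as in the earlier trial, and gain its full benefit. If that benefit covers half of follow-up on average, the effect shrinks by 1 − (1/3 × 1/2) = 5/6, from 0.333 to 0.278. If it covers all of follow-up, the factor is 2/3, giving 0.222. The non-significance rates are then about 35% and 53 to 54%. With no crossover the rate stays near 20%.

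**5. What equivalence would take (illustration).** The protocol states no margin. Assume 1.5 school days per year, a true difference of zero and 80% power. Using a 95% interval, n = 2 × 9 × (1.96 + 1.282)² = 189.1, so 190 per arm. Using a 90% interval, n = 2 × 9 × (1.645 + 1.282)² = 154.2, so 155. Both exceed 142.

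**6. Costing text side by side.** Section 9.1.1.3 says that non-significant but practically significant items are costed as well. Section 9.1.1.6 describes an analysis allowing for the same differences as a sensitivity analysis. The two can be read together (costed, then varied), but neither says which figure is the base case.

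**The case against.** The best defence is that the rule will rarely matter where it matters most. For the primary outcome at the anticipated effect, non-significance is practically impossible, and at 1 episode per year it is about 1%. The 0.33 SD figure belongs to quality of life, which enters the cost-consequences and cost-utility analyses, not the cost-effectiveness analysis. This stands and limits the size of the point. It does not remove it, because the rule is applied outcome by outcome and the protocol itself cites a benefit as low as 0.5 episodes per year.

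It can also be said that other sections soften the rule. Section 10.2.1 feeds interval estimates into the economic analysis, and section 10.2.3 names a bootstrap and incremental ratios. Neither is linked to the trigger in 9.1.1.5. The scenario work in 9.1.1.6 is for uncertainty not related to sampling variation, and its intervals for ratios do not change the trigger either.

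Three stronger readings are tempting, and the protocol does not support them:
- **That resources are costed by significance test alone.** The second limb of 9.1.1.3 admits non-significant items of practical importance, so significance is not the only gate. No figure shows that item selection would drive the incremental cost.
- **That the recommendation would be wrong 20% of the time or more.** Those are rates of missing a real difference. The cheaper care might still be the better choice, depending on costs and willingness to pay, and the protocol gives neither.
- **That the protocol concedes the two-year comparison needs a larger trial.** The remark "An equivalence trial with a substantially larger sample size would be necessary" concerns longer-term outcomes and the decision not to follow up for three years. It shows only that this is not an equivalence design.

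**Conclusion.** The point holds for the decision rule in 9.1.1.5. It turns a non-significant effectiveness result into a recommendation, with no margin or interval condition, in a trial sized for superiority. The trigger would be met despite a real difference about 20 to 21% of the time at the protocol's own 0.33 SD. For sore throats the rate is about 44% at 0.5 episodes per year, about 1% at 1 episode per year, and almost never at the anticipated effect. If one third of controls crossed over, which is an assumption, the 0.33 SD figure would rise to about 35 to 54%.

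The costing issue is secondary: an undefined threshold and an ambiguity between two sections, not a proven contradiction.

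This should be fixed. Randomisation, data collection, sample size and the primary clinical analysis are unaffected.

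**What to change.** - **Section 9.1.1.5:** delete the automatic move from non-significance to cost-minimisation and a recommendation of the cheaper care. State instead that incremental cost and incremental effect will be estimated jointly, with their uncertainty, whatever the p-value, using the bootstrap already named in section 10.2.3. Base the conclusion on that joint estimate, for example through incremental net benefit or an acceptability curve. Say which outcome governs if the outcomes point in different directions.
- **Sections 9.1.1.3 and 9.1.1.6:** reconcile them by putting all collected resource items in the base-case cost regardless of significance, and keep sensitivity analysis for uncertain unit costs and assumptions.

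The cost is a change of wording plus modest extra costing and bootstrap work on data already being collected. No additional children or follow-up are needed.

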9.1.1.6 Sensitivity analysis

To handle uncertainty not related to sampling variations and to enhance the generalisability of the results, one-way; multi-way and extreme scenario analysis will be undertaken as appropriate and confidence intervals for cost-effectiveness ratios will be estimated under different scenarios ⁴³. A sensitivity analysis taking into account differences in resource use which are practically significant (i.e. potentially costly) but which have not been shown to be statistically significant, will also be undertaken. The sensitivity analysis will also make explicit all the simplifying assumptions made to collect the data⁴⁴.

The application of discounting to the benefits will also be tested in the sensitivity analysis, as well as a range of discount rates. Particular attention will also be given to whether the costs data used reflect the true marginal opportunity costs of the resources used. When more than one reliable source of information is available, such data will be used as a term of comparison. The use of different costing methods for multi-centre studies will be explored.

Earlier studies²⁸⁻³¹suggest that longer term outcomes such as reduction in recurrent sore throat may show only marginal benefits. An equivalence trial with a substantially larger sample size would be necessary to capture significant longer-term outcomes. To contain the cost of the trial we have not proposed a three year follow up. However, the future sequence of clinical events and economic impact will be modelled beyond 2-year follow-up. The relevant data will be derived from studies which will be available and experts' opinions.

9.1.2 Measuring participants' preferences and utilities

There is a need to value the effectiveness of interventions taking account of the risk of surgery and its long-term sequelae (e.g. sleep, eating, speech, disturbances, regressive behaviour⁴⁵). The utility assessments will also provide insight into informed choice models⁴⁶.

Older children's and carers' values will be used to elicit preferences for trade-off between the perceived risks and benefits of surgery versus drugs treatment. Preferences will relate to temporary and chronic scenarios associated with morbidity and QoL because of symptoms and treatment complications. The scenarios will be developed selecting the health outcomes and QoL domains relevant to the problem. Interviews will be carried out with a sample of older children and carers from 2 of the otolaryngology departments (Newcastle and Glasgow) and the Standard Gamble method⁴⁷ will be used to derive utilities. See Appendix 2.

9.2 Data handling and record keeping

Only anonymised non-identifiable data will be recorded by the site's research teams from personal medical records. Health diaries and follow-up questionnaires will be anonymous and returned to the trial centre in reply-paid envelopes. For linking purposes these data sets will have unique study identifiers. Only the lead researcher, trial manager and trial administrator will have access to the key which links study identifiers to individual data sets. Personal details (participants full name and address) will be stored on a secure database at CHSR for the prupose of sending out questionnaires and diaries centrally. All data held for analysis will be held in accordance with the Data Protection Act. On completion of the study and associated dissemination the Trial Master File will be archived in the CHSR for 10 years. Trial sites will be responsible for archiving their own documentation.

10 Statistical considerations

10.1 Sample size calculation

In this trial we anticipate a fairly large difference in the primary clinical outcome (the reported number of episodes of sore throat in the two years after randomisation) with an effect size of around 1.0, but a smaller difference in a number of psycho-social outcomes including health-

related quality of life, with an effect size of 0.33. No standard sample size formula is available for economic evaluations, and a number of methods have been proposed ⁴⁸⁻⁵⁰. The information which is currently available limit the use of such methods in practical applications. Published data¹⁸ suggest that tonsillectomy may lead to a reduction of approximately 1.5 days per year in missed schooling. Given a reported standard deviation of 4.5, to detect this difference with 80% power we would need approximately 142 children in each arm of the trial assuming a significance level of 5%. A sample size of 142 children in the cohort group will allow us to detect similar differences between the cohort group and propositi.

The sample will be stratified by age. With a total of 284 children, we will have approximately 47 randomised to each treatment arm in each strata. Given that the standard deviation of the number of sore throats per year is estimated at approximately 2.0¹⁸, we will be able to estimate the difference between treatments in each strata with a standard error of 0.41. (Equivalently we would have 90% power to detect a difference of 1.35 episodes of sore throat per year in each strata assuming a type 1 error of 0.05).

It is anticipated that the difference in outcome between the two arms of the trial will be approximately 2 episodes in the second year of follow up. A sample size of 142 children in each arm should enable us to measure this difference with sufficient precision to undertake a meaningful economic analysis.

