The Scottish National Tonsillectomy Audit² showed high levels of patient satisfaction and that 80% of subjects did not consult a doctor in the subsequent 12 months. However, over the past 30 years a number of controlled studies with longer follow-up indicate marginal and diminishing levels of clinical benefit over a period of non-intervention. There are no substantial claims for the benefit of childhood tonsillectomy after 2 years. Roos²⁸ assessed the benefit to be 1 to 1.5 fewer sore throats (0.5 to 1 episode per annum) over the first 2 years after surgery in those with 3 to 4 episodes per annum preoperatively. Other studies²⁹⁻³¹ showed benefits of the order of ~1.5 fewer sore throats versus controls in the first postoperative year and on average single fewer episode in the second year. All of these and other available studies provide inadequate evidence because of poor definition of entry and outcome criteria, failure to include intention to treat calculations and small or skewed samples³². Even the only scientifically acceptable study by Paradise and colleagues¹⁸ suffered from comparatively small numbers of a skewed population of more severely affected children. The benefits of surgery were more marked (approximately 1.75 fewer episodes in year 1, 1.5 in year 2) but equally short lived. The drop out rate was 34% by the end of year 2 and 1 in 3 of the control group underwent surgery and were excluded from analysis. Also, the very active therapy of the control arm may have mitigated any impact of surgery. The Paradise group went on to study a more typical i.e. less severely affected group of children, but the full results of this study, near completion in 1992 have never been reported. Weight gain is a cited supplementary benefit of tonsillectomy. Two recent studies showed accelerated weight gain postoperatively, but as the children were shown to be of normal or above average height and weight preoperatively, this effect may be undesirable³³. There appears so far to be only minimal additional benefit from adenoidectomy or adenotonsillectomy in recurrent acute otitis media¹⁷.

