A straw poll, for this protocol, of consultant otolaryngologists asked: what level of reduction in sore throat would justify removal of the tonsils? Replies were remarkably consistent - at least 2 sore throats fewer per annum. No published trial to date shows a benefit of this magnitude, even in the first year after surgery. There is a pressing need for a UK, pragmatic trial to evaluate the cost-effectiveness of childhood tonsillectomy.

2 Objectives and purpose

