10.2 Statistical analysis

10.2.1 Main analysis

An intention to treat analysis will be performed. In particular, children randomised to nonsurgical conventional medical treatment will be retained in that group for the analysis even if they subsequently receive a tonsillectomy.

The primary clinical outcome measure will be the number of episodes of sore throat. This variable will be analysed using generalised linear modelling assuming a Poisson error structure with a log link function⁵¹. By fitting the difference between the two experimental groups as a fixed effect, interval estimates of the effect of tonsillectomy (in each of the first two years of follow up) will be generated. These estimates will then be used in the economic analysis.

The same approach will be used to analyse the other outcomes. A Poisson error structure will be assumed for data in the form or a count (such as the number of episodes of absence from school) and normal error structure adopted for continuous variables (such as the quality of life indices).

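### The 80% power in section 10.1 holds only if the intention-to-treat difference in missed schooling is itself 1.5 days, and the second-year sore-throat figure exceeds the evidence in section 1.3

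*Protocol*

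**What the plan says.** Section 10.1 of the protocol says that published data (reference 18) "suggest that tonsillectomy may lead to a reduction of approximately 1.5 days per year in missed schooling". It continues "Given a reported standard deviation of 4.5" and concludes that "to detect this difference with 80% power we would need approximately 142 children in each arm of the trial", at a 5% level. Section 4.3 raises the resulting 284 completers to 406 recruits for 30% attrition and allows for nothing else.

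Section 1.3 describes the study in reference 18: "1 in 3 of the control group underwent surgery and were excluded from analysis". In this trial, by section 10.2.1, control children "will be retained in that group for the analysis even if they subsequently receive a tonsillectomy". Section 13 acknowledges that surgery remains open to the control arm.

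Section 10.1 also claims 90% power in each age stratum for 1.35 episodes of sore throat per year, and an effect size of 0.33 for psycho-social outcomes. It then says: "It is anticipated that the difference in outcome between the two arms of the trial will be approximately 2 episodes in the second year" of follow-up. On a reduction of 2 per year, section 1.3 says: "No published trial to date shows a benefit of this magnitude, even in the first year after surgery".

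**The concern.** The planned effect and the planned analysis describe different quantities. A difference estimated after dropping controls who had surgery is carried into a trial that will count those children as controls. If surgery works and some controls have it, the intention-to-treat difference is smaller than the effect without crossover. The attrition allowance does not help, because crossovers are analysed and not lost.

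This has consequences for conclusions. Section 9.1.1.5 moves, depending on the outcome measure, to a cost-minimisation framework and recommends the cheaper care when there is no statistically significant evidence of a difference in effectiveness. A non-significant psycho-social result read as coming from a comparison with 80% power would carry more weight than it deserves.

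The second-year sore-throat figure is a separate fault. Section 10.1 uses it to support the claim of enough precision for a meaningful economic analysis, yet it is larger than any second-year benefit the protocol cites.

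**Working it through.** **Inputs.** From section 10.1: difference 1.5 days per year, SD 4.5, 142 per arm, level 5% (two-sided reproduces the figure; one-sided would give 112); sore-throat SD 2.0 per year; about 47 per arm per stratum; psycho-social effect size 0.33. From section 4.3: 30% attrition. From section 1.3: one third of controls crossed over in reference 18. This last rate is an assumption here, since the protocol forecasts none for its own trial.

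**The plan's own figures.** n per arm = 2(1.96 + 0.842)² × (4.5/1.5)² = 141.3, rounded up to 142. Recruitment is 284/0.7 = 406. Both reproduce.

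**Power with crossover.** Let c be the share of control follow-up time spent after surgery. Assume that 1.5 days is the effect without crossover and that a crossover gains the full benefit from then on. The intention-to-treat difference is 1.5(1 − c), and power = Φ(difference/SE − 1.96), with SE = 4.5 × √(2/142) = 0.534.

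| Crossover | c | Difference (days) | Power |
|---|---|---|---|
| None | 0 | 1.50 | 80% |
| 10% dilution | 0.10 | 1.35 | 71% |
| One third, spread evenly over 24 months | 1/6 | 1.25 | 65% |
| One third, early | 1/3 | 1.00 | 46% |

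The extra control-arm variance from mixing the two kinds of children changes the last two rows by less than one percentage point. For scale only, 80% power would need 204 per arm at 1.25 days and 318 at 1.0 day. For the effect size of 0.33, power goes from 79% to 64% (c = 1/6) and 46% (c = 1/3).

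**Primary outcome, same dilution.** With SD 2.0:
- Overall, SE = 2.0 × √(2/142) = 0.237. A difference of 1.35 becomes 1.125 (c = 1/6) or 0.90 (c = 1/3), with power 99.7% or 96.7%.
- Per stratum, SE = 2.0 × √(2/47) = 0.41, as the protocol states. Power for 1.35 is 90.5% without crossover, 78% at c = 1/6 and 59% at c = 1/3.

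**Second-year benefit.** Section 1.3 gives about 1 fewer episode in earlier controlled studies, 1.5 in the severely affected children of reference 18, and 0.5 to 1 per year in the lowest study. None reaches 2.

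**Precision.** The 95% CI half-width for a yearly difference is 1.96 × 0.237 = 0.47 episodes. That is 23% of an effect of 2, 31% of 1.5 and 47% of 1.0.

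**Two-year effect size.** Section 10.1 attaches its effect size of around 1.0 to episodes over two years. With a yearly SD of 2.0, the two-year SD lies between 2.0 × √2 = 2.83 (years uncorrelated) and 4.0 (perfectly correlated).
- Reference 18: 1.75 + 1.5 = 3.25, so 0.81 to 1.15.
- Other controlled studies: 1.5 + 1.0 = 2.5, so 0.63 to 0.88.
- Lowest study: 1 to 1.5 in total, so 0.25 to 0.53.

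**The case against.** The calculation contains no arithmetic error. It is conditional on a 1.5-day difference, and on that condition it is right. That stands: the fault is an unstated assumption about crossover.

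The direction of the bias is also not certain. Section 1.3 says that the very active control treatment in reference 18 may have reduced the apparent benefit of surgery, whereas section 6.2 prescribes usual GP care with no active protocol. That could make the difference here larger. Excluding crossovers may itself have biased the source estimate either way. The one-third rate comes from more severely affected children, and the 46% end requires nearly all crossover to happen close to randomisation. These points stand, and they make 46-65% a conditional range and not a forecast.

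A reader might infer that the trial is underpowered for its main result. The documents do not support this. Missed schooling is a social-cost measure in Table 2, neither the primary outcome nor a listed secondary clinical outcome, and the overall primary comparison keeps at least 97% power for 1.35 episodes per year.

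A reader might also infer that the effect size of around 1.0 is contradicted and should become 0.25-0.75. That range divides yearly differences by a yearly SD. On the two-year scale used in section 10.1, reference 18 supports about 0.8-1.15. Nor does absolute precision depend on the effect: the half-width is 0.47 whatever the true difference, and only its relative size changes.

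**Conclusion.** Two points hold.

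First, the 80% for missed schooling and the 90% per age stratum are true only for differences that survive crossover in an intention-to-treat analysis. Section 10.1 does not say so, although the effect on which it sizes the trial comes from an analysis that removed crossovers. Power for missed schooling would be about 65% or 46%, and per-stratum power about 59-78%, if one third of controls have surgery, the planned effect is the effect without crossover, and surgery brings its full benefit at once. The psycho-social outcomes behave like missed schooling. Less active control care could offset some of this.

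Second, the 2 episodes anticipated in the second year conflict with section 1.3 regardless of any crossover assumption.

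Neither point undermines the overall primary comparison or the choice of intention to treat. Both should be corrected in the text, because the cost-minimisation rule in section 9.1.1.5 gives weight to non-significance.

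**What to change.** Keep 142 per arm and the intention-to-treat analysis. In section 10.1:

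- State that the 80% for 1.5 days, and the 90% per stratum for 1.35 episodes, refer to the intention-to-treat difference.
- Give power over a stated range of crossover, for example c = 0, 0.10, 1/6 and 1/3 as tabulated above, and say that the one-third rate is borrowed from reference 18.
- Replace the second-year figure with about 1.0-1.5 episodes, noting 0.5-1 per year in the lowest cited study.
- State the precision as a 95% CI half-width of about 0.47 episodes per year, which is about 31-47% of an effect of 1.5-1.0.
- If the two-year effect size is discussed, report it by source: about 0.8-1.15 from reference 18, 0.6-0.9 from the other controlled studies and 0.25-0.5 from the lowest.

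A complier-average estimate beside intention to treat is optional and not needed for this correction. The cost is a few revised sentences and less favourable stated figures, with no extra children and no change to follow-up or care.
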